5.5 Use of radiation: N/A

5.6 Use of Center for Magnetic Resonance Research: This study will be approved by the CMRR (PARS) Project Application Review System.

6.0 Data and Specimen Banking

6.1 Storage and Access: Only research staff will have access to subject information. Data contained on paper records and computer files will not include names or other identifying information of subjects. Records containing identifying information will be stored in a private research office in a locked file cabinet and be accessible only by the principal investigator and the study coordinator. The study coordinator or the principal investigator will review and remind research staff of this guideline on a regular basis. Paper and electronic records will be kept for 3 years or longer. Paper records not under use will be stored in locked file cabinets in a private research space. Any identifying information on magnetic or optical media will be stored in a similar manner or be password protected. The password for accessing this information will be available to only select staff that need access to the information to conduct their research duties. All other data will not contain identifying information. All other data will be stored on encrypted magnetic or optical media that is secured or on computer systems accessible only by research staff and computer system administrators via password. There is a slight possibility that data (without identifiers) will be requested by reviewers and other scientists when study data is presented to the scientific community

6.2 Data: All diagnostic and other sensitive data will be kept in a locked file and be available only to authorized investigators involved in this study. Identifiers will include name, birthdate, address, and telephone numbers. The PI will keep the data file containing the link between subject number and identity. This will be kept in a password-protected computer file and also in printed form in a locked file cabinet. Research staff will have access to the identifiers only after a subject has agreed to participate in the study. They will use this information only for making contact to schedule visits, etc.

6.3 Release/Sharing: The data collected may represent a unique resource for some investigators. Following HHS/CDC (Department of Health and Human Services/Centers for Disease Control and Prevention) policy, we will make the de-identified data available to interested investigators who contact us for access to the data. As the proposed work is a clinical trial, the most appropriate database for our collected data appears to be clinicaltrials.gov. The investigator, co-investigator, and research staff will permit trial-related monitoring, audits, IRB/IEC(s) review and regulatory inspection(s) by providing direct access to source data/documentation.

7.0 Sharing of Results with Participants

No results are shared with participants.

8.0 Study Population

8.1 Inclusion Criteria: Participants will have a current diagnosis of OUD, be age 18-60 years, be enrolled in a methadone or buprenorphine treatment program in Hennepin Healthcare and be clinically stable. We will recruit individuals who have been in treatment with methadone or buprenorphine for at least 2 months. Inclusion criteria: (i) ability to provide written consent and comply with study procedures; (ii) meet the Diagnostic and Statistical Manual of Mental Disorders (DSM-V) diagnostic criteria for OUD. Subjects may have current comorbid drug use, but their primary substance use disorder diagnosis needs to be based on opioid use. Subjects must have the intention to remain in the methadone or buprenorphine treatment program until the end of the intervention portion of the study. Vulnerable populations will not be included.

8.2 Exclusion Criteria: Any medical condition or treatment with neurological sequelae (i.e. stroke, tumor, loss of consciousness>30 min, HIV); (ii) a head injury resulting in a skull fracture or a loss of consciousness exceeding 30 minutes (i.e., moderate or severe TBI); (iii) any contraindications for tDCS or MRI scanning (tDCS contraindication: actively receiving treatment for seizures or epilepsy; MRI contraindications; metal implants, pacemakers or any other implanted electrical device, injury with metal, braces, dental implants, non-removable body piercings, pregnancy, breathing or moving disorder); (iv) current active psychosis or mania; (v) presence of a condition that would render study measures difficult or impossible to administer or interpret (e.g. current mania, active psychosis); (vi) age outside the range of 18 to 60; (vii) primary current substance use disorder diagnosis on a substance other than opioid except for caffeine or nicotine; (viii) have current significant stimulant use (stimulant use greater than 10 days in the 30 days prior to enrollment) (ix) history of ECT or cortical energy exposure within the past 12 months, including participation in any other neuromodulation studies, (x) prisoners. Nicotine use will be recorded.

The study staff person will thoroughly describe the study and read the consent form. Then the patient will be given time to read the consent form and ask questions of study staff. If the patient agrees they will sign the consent with the study staff person looking on. Part of the consent involves asking questions of the patient via the UBACC form and having him or her record their responses to ensure they understand the study and that they can terminate participation at any point. To protect vulnerable populations, if the patient does not seem to fully understand the nature of the study (including procedures, risks, confidentiality, voluntary nature), they will not be included in the study. They are also informed that study staff may terminate study participation at any point if they are concerned about the patient's welfare or behavior.

8.3 Screening: Individuals will be screened using an IRB approved screening questionnaire that asks about demographics, type of substance use, clinical and psychiatric history, and MRI compatibility. If they do qualify for the study, they are asked if they are still interested in participating, and informed consent process starts. After informed consent, individuals will complete a screening questionnaire for contraindications of MRI scanning. Any affirmative responses on the questionnaire will result in an interview regarding the possible contraindication. CMRR staff will need to approve any affirmative response before a participant can undergo MRI scanning. Female subjects in child-bearing years will be informed that their consent to participate indicates that they are willing to complete a urine pregnancy test to demonstrate that they are not pregnant.

9.0 Vulnerable Populations

9.1 Vulnerable Populations:

- Children
- Pregnant women/Fetuses/Neonates
- Prisoners
 - Adults lacking capacity to consent and/or adults with diminished capacity to consent, including, but not limited to, those with acute medical conditions, psychiatric disorders, neurologic disorders, developmental disorders, and behavioral disorders
 - Approached for participation in research during a stressful situation such as an emergency room setting, childbirth (labor), etc.
 - Disadvantaged in the distribution of social goods and services such as income, housing, or healthcare
 - Serious health condition for which there are no satisfactory standard treatments
 - Fear of negative consequences for not participating in the research (e.g. institutionalization, deportation, disclosure of stigmatizing behavior)

PROTOCOL TITLE: Combining Neuro-Imaging and Non-Invasive Brain Stimulation for Clinical Intervention in Opioid Use Disorder

VERSION DATE: 2022-02-11

- Any other circumstance/dynamic that could increase vulnerability to coercion or exploitation that might influence consent to research or decision to continue in research
- Undervalued or disenfranchised social group
- Members of the military
- Non-English speakers
- Those unable to read (illiterate)
- Employees of the researcher
- Students of the researcher
- None of the above

9.2 Additional Safeguards:

- Study will recruit individuals (18-60 years old) who have been in treatment with methadone or buprenorphine for at least 2 months. Recruited individuals will meet DSM-V criteria for opioid use disorder (OUD; a psychiatric disorder). Potential participants will self-identify based on response to a flyer posted on IRB approved boards within the treatment program.
- Opioid use disorder is considered a psychiatric disorder, capacity to consent will be evaluated thoroughly by research staff as detailed below. Potential participants may have a lifetime psychiatric diagnosis (e.g. Anxiety or depression, not psychosis) that is under stable treatment or medication.
- Part of the consent involves asking questions of the subject and having him or her record their responses to ensure they understand the study and that they can terminate participation at any point. Participants are explained the study in detail before giving informed consent and evaluated on their capacity to consent with a form that contains the following items:
 - Participant was given time to review the consent form
 - The Consent document was explained, discussed, and reviewed
 - Study explanation and discussion was completed (check all that apply)
 - The participant's comprehension was assessed to ensure that he/she understands the research and the risks and benefits involved in the study
 - Participant's questions were answered satisfactorily and concerns were addressed
 - Upon completion of conversation, participant did not have any additional questions or concerns
 - The participant has agreed to participate in the study, and has signed and dated the most current,
 - IRB-approved consent form prior to the start of any study procedures.
 - Written consent was obtained with most recent IRB approved consent form
 - Participant was given a copy of the consent form
 - The original signed and dated consent form was placed in the research record or participant study binder
- To protect vulnerable populations, if the patient does not seem to fully understand the nature of the study (including procedures, risks, confidentiality, voluntary nature), they will not be included in the study.

PROTOCOL TITLE: Combining Neuro-Imaging and Non-Invasive Brain Stimulation for Clinical Intervention in Opioid Use Disorder

VERSION DATE: 2022-02-11

- They are also informed that study staff may terminate study participation at any point if they are concerned about the patient's welfare or behavior.
- Importance of knowledge to be gained: There are increasing data supporting specific cognitive and brain functional connectivity abnormalities in opioid use disorder. An understanding of whether these specific abnormalities can be modulated with cognitive training and non-invasive brain stimulation interventions will hold significant promise in designing new targeted interventions that can reduce vulnerability to relapse and improve treatment outcome.
- Protection Against Risk. Trained research staff will be instructed to keep the content of the records confidential. During the initial consent process subjects will be told that they have the right to refuse to answer questions; however, this may affect whether they continue in the study. At all points in the study subjects will be warned at the beginning of procedures which involve the disclosure of personal and sensitive information. These warnings will occur in the introductory comments of interviews or in the instructions of questionnaires and surveys.
- Importance of Knowledge Gained. The knowledge derived from this research will allow us to gather crucial evidence supporting the therapeutic use of interventions targeting both cognitive and underlying neural mechanisms that support abstinence. The knowledge gained from this study may eventually help guide further research in the area and future studies to improve addiction treatment programs.
- Recruitment will conform to HIPAA requirements regarding protection of private health information.
- To protect vulnerable populations, if the patient does not seem to fully understand the nature of the study (including procedures, risks, confidentiality, voluntary nature), they will not be included in the study. They are also informed that study staff may terminate study participation at any point if they are concerned about the patient's welfare or behavior.
- After detailed informed consent, participants' capacity is further evaluated with the UCSD Brief Assessment of Capacity to Consent (UBACC).
- No neonates, prisoners, individuals who have not attained legal age for consent.

10.0 Local Number of Participants

10.1 Local Number of Participants to be Consented: Up to 250

11.0 Local Recruitment Methods

11.1 Recruitment Process:

- (1) Patients enrolled in a methadone or buprenorphine treatment program in the Twin Cities Area (such as Hennepin Healthcare and VA Medical Center) will learn about the study through an IRB-approved brochure or flyer posted on a board . Participants will also learn about the study via word of

PROTOCOL TITLE: Combining Neuro-Imaging and Non-Invasive Brain Stimulation for Clinical Intervention in Opioid Use Disorder

VERSION DATE: 2022-02-11

mouth at their treatment program. Participants will self-identify and call research staff to learn more.

- (2) Clinical staff colleagues will inform patients about the study via a recruitment card or brochure if he or she believes it would be beneficial to the patient. These participants will call research staff to learn more if interested.
- (3) Study staff will post advertisements online and paper flyers in community publications. Participants will self-identify and call research staff to learn more.
- (4) Patients enrolled in a methadone or buprenorphine treatment site who agree to do study recruitment (such as Hennepin Healthcare) will learn about the study via a displayed tablet paired with the words “Research Opportunity”. If a patient is interested in learning more about participation in the study, they are directed to complete the opt-in REDCap form on the tablet. Research staff will review the survey and call the participant back with an eligibility decision or more information.
- (5) Patients enrolled in a methadone or buprenorphine treatment site will be sent mail ads for the study.

If a patient is interested in participating in the study, they are instructed to call research staff. During this first contact call, patients are given general information about the study and if patients want to learn more about the study and to find out if they qualify to be in it, a phone appointment or in-person appointment is set up to meet research staff at a specific date and time. At this appointment, research staff will give the patient detailed information about the study. If participants are still interested in participating in the study after learning all details of the study, research staff will ask them if they would like to answer confidential questions to determine if they qualify to be in the study.

If participants do not qualify to be in the study, research staff will thank them for their time and tell them the general reasons why they do not qualify to be in the study. If participants do qualify to be in the study, research staff will let them know that they do qualify to be in the study and ask them if they are still interested to be in the study. If so, research staff will proceed with enrollment (e.g. consent, HIPAA, etc.).

A trained and IRB-approved study staff person will carry out the consent process. The subject will be given time to read the consent form and to ask questions. If the subject agrees they will sign the consent form with the study staff person looking on. Part of the consent involves asking questions of the subject and having him or her record their responses to ensure they understand the study and that they can terminate participation at any point. They are also informed that study staff may terminate study participation at any point if they are concerned about the subject's welfare or behavior.

PROTOCOL TITLE: Combining Neuro-Imaging and Non-Invasive Brain Stimulation for Clinical Intervention in Opioid Use Disorder

VERSION DATE: 2022-02-11

11.2 Identification of Potential Participants: Individuals with opioid use disorder (OUD) will be recruited via the methods described in 11.1. We will monitor recruitment progress and expand outreach goals to other clinics if we are not meeting project targets. Clinic staff will not be involved in the intervention.

Participants will not be recruited based on information contained in private/protected records.

- No private/protected records will be used.
- Potential participants will self-identify and express their interest after learning about the study on IRB approved materials in the treatment program, word of mouth, community referral, or referral via clinical staff colleague.
- MEDICAL records will be used to send recruitment letters, in a manner as approved by the partner treatment site (e.g. MHealth Fairview)
- HIPAA form states that the participant does agree to have research staff communicate with treatment program staff that they are participating in research.

11.3 Recruitment Materials: Participants will see a flyer posted (uploaded to Ethos) in poster boards within the treatment program. If interested, participants call phone number in flyer to set up an in-person informational/screening appointment.

11.4 Payment: Participant compensation will be provided according to the schedule below:

- Screening/Visit 1: \$10 for screening evaluation; \$25 for completing baseline questionnaires
- Visits 2-3: \$25 for completion of pre-intervention assessments; \$25 for completion of MRI scan
- Visits 4-8: \$15 for tDCS interventions (up to \$75)
- Visit 9-10: \$25 for completion of midpoint assessments; \$25 for completion of MRI scan
- Visits 11-15: \$15 for tDCS interventions (up to \$75)
- Visits 16-17: \$25 for completion of post-intervention assessments; \$25 for completion of MRI scan
- Follow-up visit 1: \$50
- Follow-up visit 2: \$50

The total amount a participant could receive if he/she completes all study visits and activities is \$435.

PROTOCOL TITLE: Combining Neuro-Imaging and Non-Invasive Brain Stimulation for Clinical Intervention in Opioid Use Disorder

VERSION DATE: 2022-02-11

12.0 Withdrawal of Participants

12.1 Withdrawal Circumstances: Participants will be able to discontinue study participation at any time. The participants may choose to discontinue stimulation at any time during the session if experiencing excessive discomfort or side effects. Criteria for discontinuation related to intervention: i) sores at the tDCS administration site; ii) headaches that impair global functioning. If subjects choose to stop their participation, they will be released from the study. To protect vulnerable populations, if a patient that was deemed capable of providing consent goes through unforeseeable situations that may affect their capacity to consent, their capacity will be reassessed, and if not deemed capable, they will be withdrawn from the study. Participants are also informed that study staff may terminate study participation at any point if they are concerned about the patient's welfare or behavior.

12.2 Withdrawal Procedures: Participants will be withdrawn from the study if they report any side effects of greater than moderate severity or that raise any safety concerns. Subjects may also be withdrawn from the study if they fail to follow study procedures (e.g., show up to scheduled study visits). Additionally, subjects will be told that participation is voluntary and that they may discontinue participation at any time for any reasons.

If participants withdraw from procedures, all their data collected until the withdrawal data will be retained. No new data will be collected from any private/protected record.

Participants who withdraw from the study after having received tDCS will be asked if they can be contacted by telephone to ascertain substance use status. We will attempt to contact participants by telephone who do not show up to scheduled visit to ascertain if they wish to continue to participate in the study (and if not, why not) and to determine substance use status.

12.3 Termination Procedures: If at any point research staff is concerned about participant's welfare or behavior, they will notify the participant that their participation in the study needs to terminate because of safety reasons. The participant will be paid for their time as per 11.4 until their last active participation day. Data collected until the termination date will be used and considered incomplete.

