3.0 Study Endpoints/Events/Outcomes

3.1 Primary Endpoint/Event/Outcome: In a double-blind randomized design, up to 250 individuals with a current opioid use disorder (OUD) diagnosis, age 18-60 years, enrolled in a methadone or buprenorphine treatment program and

PROTOCOL TITLE: Combining Neuro-Imaging and Non-Invasive Brain Stimulation for Clinical Intervention in Opioid Use Disorder

VERSION DATE: 2022-02-11

clinically stable will be recruited. We will recruit individuals who have been treatment with methadone or buprenorphine for at least 2 months. Patients will receive 10 sessions (2 5-day blocks of 46-minute daily tDCS intervention) of either (i) transcranial direct current stimulation (tDCS) to PFC or (ii) sham-tDCS. All subjects will perform cognitive training during tDCS intervention (active or sham) to prime the engagement of the NAcc-PFC brain circuit. Rest fMRI will be collected pre-intervention, after 5 sessions, and post-intervention. Follow-up interviews will be conducted 1- and 2-months after intervention completion to assess cognition, assess behavior, and query substance use. Dependent variables will be (i) change in NAcc-PFC FC across intervention imaging sessions, (ii) change in cognitive performance across intervention sessions, and (iii) substance use status 2 months after study participation. The Specific Aims are to determine if the intervention: (A1) is feasible and safe in individuals with OUD, (A2) induces circuit-based target engagement (an NIH funding requirement), (A3) induces cognitive performance changes, and (A4) is related to substance use status 2 months after study.

To evaluate feasibility (A1), withdrawal and retention policies are described in Section 12.0. To evaluate safety (A1), we will use the Treatment Side Effects Questionnaire to record intervention side effects. Based on our alcohol tDCS study and studies from other research groups, we hypothesize that the intervention will be feasible and safe.

To evaluate circuit-based target engagement (A2) we will compare brain activation change (from pre-intervention to post-intervention) between active tDCS and sham groups. We hypothesize that the active tDCS group will have a larger increase in brain circuit engagement than the sham group.

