To evaluate cognitive performance changes (A3), we will compare cognitive performance change from pre-intervention to post-intervention) between active tDCS and sham groups. We hypothesize that the active tDCS group will have a larger improvement in cognitive performance than the sham group.

To evaluate substance use status during participation and 1- and 2-months later (A4), we will administer the Timeline Follow Back(Sobell and Sobell 1996) questionnaire, assess the number of days of opioid use, and amount at peak use at follow-up (1- and 2-months later). We will also collect saliva/urine samples as often as every week. Based on our alcohol pilot study and literature on the effect of tDCS in other addictions (Lupi et al. 2017; Batista et al. 2015), we hypothesize that the active tDCS group will have lower followup substance use rates and longer abstinence periods than the sham group.

3.2 Secondary Endpoint(s)/Event(s)/Outcome(s): To determine generalization and durability of cognitive training, patients will be asked to complete the following tasks at pre-intervention, post-intervention, 1-month follow-up and 2-

PROTOCOL TITLE: Combining Neuro-Imaging and Non-Invasive Brain Stimulation for Clinical Intervention in Opioid Use Disorder

VERSION DATE: 2022-02-11

month follow-up to examine generalization and durability effects of training: D-KEFS Trail Making Test, D-KEFS Verbal Fluency, D-KEFS Color Word, Digit-Span (WAIS-WISC), Digit Symbol (WAIS-WISC).

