The participant will also undergo a pre-intervention MRI, lasting about 2 hours. The MRI involves taking pictures of the participant's brain, from which the properties of certain brain tissues can be measured. While sometimes MRI scans are done for clinical purposes, the scans the participant will receive are being done for research purposes. Since these scans are not designed for clinical or medical reading, the participant's scans will not receive a clinical or medical interpretation. For the scan, the participant will be asked to lie down quietly on a bed, and the bed will slide into the scanner. Once the participant is inside the scanner, it will start to take the pictures. During the scan, the participant will simply lie quietly in the scanner with eyes closed while the scanner takes images of the participant's brain. The MRI scan will be performed at the University of Minnesota's Center for Magnetic Resonance Research.

The assessment visit may be performed before, same-day, or after the MRI visit for ease of accommodating the schedule of the scanner or participant.

VISITS 4-8: Will involve cognitive training tasks concurrently with tDCS, with tDCS for the first 20 minutes (46 minutes total per day). We will first explain to the participant what the training tasks entail and detail tDCS procedures. TDCS side-effects questionnaire will be administered daily before and after intervention.

During tDCS intervention (active) the participant will be seated in a reclining chair while the participant perform the reversal learning task. Total participation time for visits 4-8 will be about 1 hour each day, or about 5 hours over a period of 2 weeks.

VISITS 9-10/MIDPOINT: At the midpoint assessments and MRI, the participant will be administered the same cognitive assessments, and substance use questionnaires as Visit Two. Craving will be re-assessed and follow-up MRI scan with same procedures as Visit Three will be collected. Total participation time for Visits 9-10 will be about 4 hours.

PROTOCOL TITLE: Combining Neuro-Imaging and Non-Invasive Brain Stimulation for Clinical Intervention in Opioid Use Disorder

VERSION DATE: 2022-02-11

The assessment visit may be performed before, same-day, or after the MRI visit for ease of accommodating the schedule of the scanner or participant.

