VISITS 11-15: Will involve cognitive training tasks concurrently with tDCS, with tDCS for the first 20 minutes (46 minutes total per day). We will first remind the participant what the tasks entail and detail tDCS procedures. TDCS side-effects questionnaire will be administered daily before and after intervention.

During tDCS intervention (active or sham) the participant will be seated in a reclining chair while the participant perform the reversal learning task. Total participation time for days 3-7 will be about 1 hour each day, or about 5 hours over a period of 2 weeks.

VISITS 16-17/POST-INTERVENTION: At the post-intervention assessments and MRI, the participant will be administered the same clinical assessments, cognitive assessments, and substance use questionnaires as Visits 9-10. Craving will be re-assessed and follow-up MRI scan with same procedures as baseline will be collected. Total participation time for Visits 16-17 will be about 4 hours.

The assessment visit may be performed before, same-day, or after the MRI visit for ease of accommodating the schedule of the scanner or participant.

IN PERSON FOLLOW-UP: The participant will be asked to return 1- and 2-months after intervention to fill out the same clinical, cognitive and substance use questionnaires that were administered on Visits 2, 9, and 16. Follow-up visits will be about 1.5 hours each. Subjects will undergo saliva/urine tests evaluating recent drug/alcohol use.

At follow-up timepoints, we will contact subjects two weeks prior to the next follow-up to coordinate scheduling with sufficient time so that data is collected as close to the target as possible.

Retention: To maximize participant retention we will have all consented participants fill out a “contact” document in which they will provide at least two telephone numbers to be reached and one home address. We will ask participants to provide the phone number of a good friend or relative who will know their whereabouts to help us re-contacting the participant if needed. Before follow-up appointments, we will call participants over the phone to confirm their attendance and we will send reminder cards through regular mail. If participants give their consent, we will also send a text to their contact phone number.

5.3 Study Duration:

- The anticipated duration an individual participant’s participation in the study is 2.5-4 months since recruitment.

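### Section 12.2 withdraws a participant from the study, not only from tDCS, after a side effect above moderate severity, and no explicit rule follows that side effect to resolution

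*Combined protocol and SAP*

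**What the plan says.** Section 12.2 is mandatory and its object is the study: "Participants will be withdrawn from the study if they report any side effects of greater than moderate severity or that raise any safety concerns". Data gathered up to withdrawal are kept. Participants who withdraw after receiving tDCS "will be asked if they can be contacted by telephone to ascertain substance use status". No other later data collection is named for them.

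Section 12.1 lets a participant stop within a session by choice: "The participants may choose to discontinue stimulation at any time during the session if experiencing excessive discomfort or side effects". It then gives two criteria for discontinuation related to the intervention: sores under the electrode, and headaches severe enough to impair functioning. It does not say whether someone who meets either one stays for assessments.

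Safety is part of Specific Aim A1 and is measured with the side-effects questionnaire (Section 3.1). Section 5.2, under Visits 4-8 and again under Visits 11-15, says: "TDCS side-effects questionnaire will be administered daily before and after intervention". Section 20.1 also places it after consent and on each intervention day. It is not scheduled at any later visit.

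For A2, Section 3.1 says "we will compare brain activation change (from pre-intervention to post-intervention) between active tDCS and sham groups", and A3 makes the same pre-to-post comparison for cognition. At the 1- and 2-month visits, Section 5.2 says: "Subjects will undergo saliva/urine tests evaluating recent drug/alcohol use".

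Section 17.2 requires assessment and reporting of adverse events in general terms. Section 19.1 offers care for injury. Neither mentions the outcome of a side effect after withdrawal.

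**The concern.** Stopping the stimulation protects the participant. Ending the assessments is a separate decision, and 12.2 makes both at once. The people removed are selected by how badly they tolerated the intervention.

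Two things are at stake. First, the A1 safety record stops at the events that matter most: the instrument is tied to intervention days, and the telephone contact covers substance use only. Section 2.2 says the safety of this combination has not been studied in opioid use disorder, so even one such event is informative, whatever the numbers per arm. Second, the pre-to-post change that A2 and A3 compare cannot be computed for these participants, and the missingness is related to treatment experience.

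**Working it through.** The plan states no figure on this point; Section 15.2 says a power analysis does not apply. The check is a count from the visit schedule, followed by a bounded illustration.

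**What is lost per participant withdrawn** (Sections 3.1, 3.2, 5.2)

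| Item | Scheduled | Lost, sessions 1-5 | Lost, sessions 6-10 |
|---|---|---|---|
| Scans (pre, midpoint, post) | 3 | 2 | 1 |
| Cognitive timepoints in 3.2 (pre, post, 1 month, 2 months) | 4 | 3 | 3 |
| Midpoint cognitive battery (5.2 only) | 1 | 1 | 0 |
| Follow-up saliva/urine tests | 2 | 2 | 2 |

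The midpoint cognitive row is less firm than the others. Section 5.2 says "At the midpoint assessments and MRI, the participant will be administered the same cognitive assessments, and substance use questionnaires as Visit Two", but Sections 3.2 and 5.1 list four timepoints without a midpoint. The description of Visits 2-3 mentions only questionnaires and the MRI, and the baseline battery is placed at Visit 1. The row is therefore kept apart from the 3 of 4.

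**Exposure by arm** (Section 4.0). Active: 0.5 + 20 + 0.5 = 21 minutes of current per session. Sham: 0.5 + 0.5 = 1 minute, assuming the sham ramp-down also takes 30 seconds. Withdrawal could therefore differ by arm, but this does not show that it does. Sham participants also feel the initial itching.

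**Size of a completers-only shift** (inputs assumed, not from the plan)

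- 15 completers per arm, from the amendment log's goal of 30 completers. The current text gives only a cap of 250.
- Withdrawals in the active arm only.
- Mean change in those withdrawn differs from that in completers by 0.5 to 1.0 SD.

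Shift = k/(15 + k) × difference, where k is the number withdrawn.

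- k = 1: 1/16 = 0.0625, so 0.031 to 0.063 SD.
- k = 2: 2/17 = 0.118, so 0.059 to 0.118 SD.

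Standard error of the difference = √(1/15 + 1/15) = 0.365 SD. The shift is 0.09 to 0.17 standard errors for k = 1 and 0.16 to 0.32 for k = 2.

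One check against the design: 17 + 15 = 32 is eight full blocks of 4, which would give 16 per arm. Two active withdrawals would then leave 14 against 16 completers. The weight is 2/16 = 0.125 and the shift 0.06 to 0.13 SD, which is practically the same.

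**Later assessment pay** (Section 11.4). Sessions 1-5: 50 + 50 + 50 + 50 = $200. Sessions 6-10: 50 + 50 + 50 = $150.

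**The case against.** The strongest reply is that this is a defensible conservative rule in a small pilot. The combination is untested in this population, and Section 13.1 expects adverse events to be rare and side effects mild. Section 3.1 refers feasibility to the Section 12 policies, so withdrawal is itself a result. A scan after two or three sessions reflects assignment, not a full course. All of that stands. It supports stopping tDCS promptly, but it does not require the assessments to end.

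Four stronger readings are tempting, and the documents do not support them:

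- **That the protocol forbids later scans and tests.** No sentence says so. It is inferred from the word study in 12.2 and from the telephone-only provision. The 12.1 criteria, and a phrase in 12.2 about withdrawing from procedures, leave some ambiguity between stopping tDCS and leaving. They do not create a route to stay.
- **That side-effect outcomes go unrecorded.** The questionnaire is given before and after each session, so the course within a session is normally captured. Section 17.2 carries a general duty, and Section 17.1 refers to an institutional monitoring plan that is not in the documents. What is missing is an explicit rule to follow the effect to resolution.
- **That the loss biases the comparison between arms.** The documents give no rate of effects above moderate severity in either arm.
- **That three active-arm withdrawals would shift the result further.** With 15 completers per arm this needs 18 against 15 randomised, and blocks of 4 allow an imbalance of at most 2.

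Two mitigating points also stand. Those withdrawn at sessions 6-10 normally keep the midpoint scan, which can inform the trend over time. Substance use status may still be obtained by telephone. That is voluntary self-report without a drug test, and the wording leaves open whether it covers people whom staff withdraw.

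**Conclusion.** The point holds as a design improvement with limited numerical consequence. Followed as written, 12.2 removes from all later visits the participants who tolerated the intervention worst, and the protocol has no explicit step to learn how their side effect ended. Each one lacks the post-intervention scan, three of the four cognitive timepoints in 3.2 and both follow-up drug tests. Withdrawal at sessions 1-5 also costs the midpoint scan.

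The effect on the group comparison is small: about 0.03-0.12 SD for one or two withdrawals, on assumed inputs, against a standard error of about 0.37 SD. A reader might infer a biased efficacy result; neither the documents nor this arithmetic support that. The case for change rests mainly on a complete A1 safety record, and secondarily on less selective loss for A2 and A3. It relies on the protocol text alone, since the consent pages were not available.

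**What to change.** Amend 12.2 along these lines: a participant who meets any side-effect stopping criterion, including the two in 12.1, receives no further tDCS. Unless they withdraw consent or the investigator judges the visits unsafe, they are invited to all remaining assessment, MRI and follow-up visits at the planned dates, paid as per 11.4. The side effect is followed until resolved or stable, by telephone if visits are declined.

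In the A1 text of 3.1, report stopped stimulation and left study as separate counts, by arm. Flag scans taken after a partial course. Record for each withdrawal which rule was in force.

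Cost: wording in 12.2, 3.1 and the consent form. Per participant stopped, it means 2 scans and up to $200 (sessions 1-5) or 1 scan and up to $150 (sessions 6-10), plus any assisted transport to the scanner. The pay lies within the planned $435 per person. If recruitment continues until 30 participants complete, however, these scans may come on top of the completers' scans. Some participants will decline the visits. Section 5.3 expected enrolment to end in Summer 2022, so the change reaches only those still in the study; the separate reporting for A1 can still be done at analysis.
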